Data analysis were a repeated measures analysis of variance (RM-ANOVA) to address Hypothesis 1. The basic design for these analyses was a 2x3 design with three assessment time points (the within-subjects factor) crossed with the two treatment conditions (BBTF and the comparison group [the between-subjects factor]). The null hypothesis for all these analyses was that changes for all dependent measures (psychological well-being, parenting competence, father-mother relationship quality, material support, in-kind support, and father-child interaction) would remain constant for the two groups over time. The alternative hypothesis was that they would increase over time in the BBTF group relative to the control group. This was the interaction effect in the RM-ANOVA. An initial multivariate analysis was be conducted first to see if there was any overall effect. If the null hypothesis was rejected in the multivariate analysis, we examined the univariate analyses. We tested for violations of sphericity, and if they were in evidence, then a Greenhouse-Geisser correction was used to estimate probability values.

In order to determine when these changes occurred across the three assessment time points, a follow-up analysis was conducted with time reparameterized into a set of two orthogonal Helmert contrasts. The two contrasts were of the form (1, -1/2, -1/2; 0, 1, -1), where if the first contrast was significant, this indicated that the critical differences occurred between times 1 and 2; and if the second was significant, the changes took place between times 2 and 3. This informed us as to the transition point or points where the velocity changes were greatest between the treatment and comparison groups.

Hypothesis 2: Across both conditions, father outcomes and post-intervention ratings of father-mother relationship quality will mediate paternal involvement at 12 weeks and 24 weeks.

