This analysis used a regression approach to mediation analysis, as that described in MacKinnon, 2008.¹³³ This approach looked at the extent to which changes in paternal involvement over time were explained by changes in the father outcomes and the mother-father relationship in both the treatment and control groups. This effect was estimated using a series of three regression analyses. The dependent variable (a measure of paternal involvement) at Time 2 (12 weeks) was regressed on a dummy-coded treatment variable and the same paternal involvement measure at Time 1 (baseline). Then the mediators (father outcomes and mother-father relationship) were included in the regression models, and the change in R-squared was used to determine their impact. These analyses were repeated for Times 1 and 3 (24 weeks).

Hypothesis 3a: Relative to the attention control group, BBTF children will have improved child outcomes (behavioral, emotional, and social) at 12 weeks and 24 weeks.

The analysis of Hypothesis 3a was directly parallel those described for Hypothesis 1. The only difference was in the dependent measures, which were be child outcomes instead of paternal involvement outcomes.

Hypothesis 3b: Across both conditions, father outcomes, father-mother relationship and paternal involvement will mediate child outcomes at 12 weeks and 24 weeks.

This analysis used the same regression approach to mediation analysis described in Hypothesis 2, with the only differences being that the outcome variable was the child outcomes

rather than paternal involvement; paternal involvement acted as a mediator along with father outcomes and father-mother relationship.

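### Hypothesis 3b enters a causal chain as parallel mediators and judges them by change in R-squared, so it cannot say which of the three mediates

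*Combined protocol and SAP*

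**What the plan says.** All of this is in the Data Analysis section of the combined protocol and SAP.

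- **Hypothesis 2** states that "father outcomes and post-intervention ratings of father-mother relationship quality will mediate paternal involvement at 12 weeks and 24 weeks". Its analysis looks at how far "changes in paternal involvement over time were explained by changes in the father outcomes and the mother-father relationship". Involvement is the dependent variable; the other two explain it.
- **Decision statistic.** After a regression on treatment and the baseline value of the outcome, the mediators "were included in the regression models, and the change in R-squared was used to determine their impact". No other criterion is named.
- **Hypothesis 3b** states that "father outcomes, father-mother relationship and paternal involvement will mediate child outcomes at 12 weeks and 24 weeks".
- **Its method:** "This analysis used the same regression approach to mediation analysis described in Hypothesis 2". The only differences given are the dependent variable, now child outcomes, and the mediator set: "paternal involvement acted as a mediator along with father outcomes and father-mother relationship".

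The text does not state an order of entry among the three mediators, a path running from one mediator to another, or a rule for reading the contribution of each one.

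**The concern.** Taken together, the two hypotheses imply a chain: programme, then father outcomes and relationship, then involvement, then child. Hypothesis 3b treats the three intermediate variables as equals. That leaves two ways to read its result, and neither answers the question it poses.

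Read as a block, a significant change in R-squared shows that at least one of the three is related to the child outcome. It does not show that all three mediate, which is what the hypothesis claims.

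Read by coefficient, father outcomes and relationship are adjusted for a variable that Hypothesis 2 says they influence. Their coefficients leave out whatever they pass on through involvement.

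At stake is the account of how the programme reaches the child. A report could credit all three mediators on the strength of one, or dismiss the upstream two because involvement carries their effect.

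**Working it through.** **Plan's own figures.** None is given for a mediation analysis. The one design figure (Power Analysis: d = .42, 72 per group, one-tailed alpha .05, power .80) reproduces: .42 × √(72/2) − 1.645 = 2.52 − 1.645 = 0.875, which gives power 0.81. It does not bear on this point. Two of its inputs are borrowed below: the evaluable number of 144, and .42 as the programme's effect on each upstream mediator. The second use is an assumption. All path values are also assumptions, because the documents give none, so a range is shown.

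**Step 1: what adjustment does to a coefficient.** Take father outcomes F, involvement I and child outcome C on standardised scales, with paths F→I = .4 and I→C = .4 and no direct F→C path. The correlations are r(F,I) = .4, r(I,C) = .4 and r(F,C) = .4 × .4 = .16.

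- F alone: .16
- F with I in the model: (.16 − .4 × .4)/(1 − .4²) = 0/.84 = 0
- I with F in the model: (.4 − .4 × .16)/(1 − .4²) = .336/.84 = .40

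This example has no treatment variable, so .16 is an effect of F on C and not yet a mediated effect.

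**Step 2: add treatment.** Let treatment T shift F and the relationship R by a = .42 each. Let I = bF + bR + error and C = cI + gF + gR + error, with unit residual SDs.

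- Indirect effect credited to F without I in the model: a(g + bc)
- Indirect effect credited to F with I in the model: ag
- Sum over mediators without I: 2a(g + bc)
- Sum over mediators with I: 2ag + 2abc, the same total

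| b = c | g | F, without I | F, with I |
|---|---|---|---|
| .2 | 0 | .42 × .04 = 0.017 | 0 |
| .4 | 0 | .42 × .16 = 0.067 | 0 |
| .6 | 0 | .42 × .36 = 0.151 | 0 |
| .2 | .2 | .42 × .24 = 0.101 | 0.084 |
| .4 | .2 | .42 × .36 = 0.151 | 0.084 |
| .6 | .2 | .42 × .56 = 0.235 | 0.084 |

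The joint indirect effect does not change. At b = c = .4 and g = 0 it is 2 × .0672 = 0.134 either way. Adding involvement moves credit between mediators and loses none of the total.

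**Step 3: rejection rates for the F coefficient.** These come from 2,000 simulated trials of 144, two-sided 5%, with g = 0. For b = c = .2, .4 and .6, F is significant in 7.5%, 43% and 95% of trials without I. With I it is significant in about 5% throughout, the nominal level.

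**Step 4: rejection rates for the block.** The change in R-squared is taken as an F test with 3 and 144 − 5 = 139 degrees of freedom. There were 4,000 simulated trials per setting, and repeat runs move the rates by a point or two.

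| Setting | Three-mediator block | F and R entered first |
|---|---|---|
| F and R inert, I→C = .2 | 47% | about 5% |
| F and R inert, I→C = .3 | 85% | about 5% |
| F and R inert, I→C = .4 | 98% | about 5% |
| Serial chain, b = c = .4, g = 0 | 99.7% | 60% |

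At a path of .4 the block test gives nearly the same answer whether the chain exists (99.7%) or the upstream mediators do nothing (98%). Staged entry separates the two cases (60% against about 5%). The simulations leave out the baseline covariate that the plan includes.

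**The case against.** The strongest reply is that the plan names change in R-squared as its criterion, not individual coefficients. A reader might infer that the joint model erases the upstream path, or that Hypothesis 3b cannot confirm the programme's theory. The documents do not support either inference. Step 2 shows that the joint indirect effect keeps the path, and the plan contains most of the chain already. Hypothesis 1 tests the programme's effect on all the mediators, Hypothesis 2 regresses involvement on the upstream two, and the joint Hypothesis 3b model gives the involvement-to-child path adjusted for them. That joint model is needed for a serial estimate.

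A reader might also infer that the upstream coefficients must be zero. That requires father outcomes and relationship to reach the child only through involvement, which no passage says. Naming all three as mediators of child outcomes is compatible with direct paths. With a direct path of .2 the credited effect shrinks but remains.

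Three further points stand in part:

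- Simultaneous entry is the natural reading of the wording but is not spelled out.
- The block's failure to attribute is a general limit of R-squared change and would apply to Hypothesis 2 as well. It is more serious in Hypothesis 3b, where the mediators are themselves ordered.
- The measures are taken at the same visits, so the data cannot verify an order. Staged entry takes the order from Hypothesis 2 as an assumption.

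These points limit the size of the claim. They do not supply a rule for attributing mediation among the three.

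**Conclusion.** The point holds in a limited form. Hypothesis 2 orders the mediators, Hypothesis 3b on its natural reading does not, and the stated statistic cannot say which of them mediates. A significant block is not evidence that all three do: under the assumed paths of .2 to .4 it appears in 47% to 98% of trials when only involvement matters. If coefficients are read instead, those for father outcomes and relationship understate their part by whatever passes through involvement. They are zero only in the limiting case of no direct path, and otherwise reduced.

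The sizes rest on assumed linear paths, on .42 as the programme's effect on each upstream mediator, and on 144 evaluable fathers. The structural conclusion does not depend on these values. It concerns the mechanism claim only.

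**What to change.** For Hypothesis 3b, specify the steps:

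1. Regress the child outcome on treatment and its baseline value.
2. Add father outcomes and father-mother relationship. Report their coefficients and the change in R-squared.
3. Add paternal involvement as a separate step, which gives the planned joint model. Report the fall in the upstream coefficients.
4. Report specific and serial indirect effects as products of paths, including the path from treatment to the mediator, with confidence intervals.
5. State which mediator each conclusion concerns, and note that the order among mediators measured at the same visit is assumed from Hypothesis 2.

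The data are already part of the planned collection. The cost is SAP wording, one more regression per child outcome and visit, and a longer results table. If the analyses are complete, the added step can be run and reported as supplementary.
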